#### 18.5 Peer Review

The study protocol was reviewed by the funders of the study – the National Institute for Health research HTA programme.

#### 18.6 Declaration of Helsinki and Good Clinical Practice

The study will be performed in accordance with the spirit and the letter of the declaration of Helsinki, the conditions and principles of Good Clinical Practice, the protocol and applicable local regulatory requirements and laws.

#### 18.7 GCP Training

All GLINT staff must hold evidence of appropriate GCP training or undergo GCP training prior to undertaking any responsibilities on this study. This training should be updated every 2 years or in accordance with your Trust's policy.

#### **19** Sponsorship, Financial and Insurance

The study will be sponsored by the Cambridge University Hospitals NHS Foundation Trust and the University of Cambridge. The study will be funded by National Institute for Health Research – Health Technology Assessment Programme (09/01/48).

Cambridge University Hospitals NHS Foundation Trust, as a member of the NHS Clinical Negligence Scheme for Trusts, will accept full financial liability for harm caused to participants in the study caused through the negligence of its employees and honorary contract holders. There are no specific arrangements for compensation should a participant be harmed through participation in the study, but no-one has acted negligently.

The University of Cambridge will arrange insurance for negligent harm caused as a result of protocol design and for non-negligent harm arising through participation in the clinical trial.

#### 20 Monitoring, Audit & Inspection

The investigator must make all study documentation and related records available should an MHRA Inspection occur. Should a monitoring visit or audit be requested, the investigator must make the study documentation and source data available to the Sponsor's representative. All participant data must be handled and treated confidentially.

The Sponsor's monitoring frequency will be determined by an initial risk assessment performed prior to the start of the study. A detailed monitoring plan will be generated detailing the frequency and scope of the monitoring for the study. Throughout the course of the study, the risk assessment will be reviewed and the monitoring frequency adjusted as necessary. Monitoring will be performed according to GCP. It is planned to do 100% SDV on the first 5 participants at any site. The frequency of any additional on-site monitoring will be informed by the data quality found at site and risk assessment undertaken by the sponsor. If data quality is not an issue, further on-site visits will be performed on an annual basis. To optimise resources, GLINT personnel from one site will conduct the on-site monitoring visits at another site. If there are issues with data quality the site in question will be required to complete a remedial action plan and will be re-monitored after an additional five participants.

Additional data monitoring will be carried out through data checks generated automatically through the Trial Management System Database e.g. validation data item checks which will be addressed by the study coordinators at site. Resolution of questionnaire data queries generated by the Trial Management System Database will be managed by coordinating centre clinicians/ study coordinators.

Monitoring reports will be reviewed in accordance with Sponsor SOPs.

#### 21 Protocol Compliance and Breaches of GCP

GLINT will be conducted in accordance with the current approved protocol, with the conditions and principles of GCP, relevant regulations and standard operating procedures. Prospective, planned deviations or waivers to the protocol are not allowed under the UK regulations on Clinical Trials and must not be used.

Data will be evaluated for compliance with the protocol and accuracy in relation to source documents. Following written standard operating procedures, the monitors will verify that the study is conducted and data are generated, documented and reported in compliance with the protocol, GCP and the applicable regulatory requirements.

Protocol deviations, non-compliances, or breaches are departures from the approved protocol. They can happen at any time, but are not planned. They must be adequately documented on the relevant forms and reported to the Chief Investigator and Sponsor immediately.

Deviations from the protocol which are found to occur constantly again and again will not be accepted and will require immediate action and could potentially be classified as a serious breach.

The Medicines for Human Use (Clinical Trials) Regulations contain a requirement for the notification of "serious breaches" to the MHRA within 7 days of the Sponsor becoming aware of the breach. A serious breach is defined as "A breach of GCP or the trial protocol which is likely to effect to a significant degree:

(a) the safety or physical or mental integrity of the participants of the trial; or

(b) the scientific value of the trial".

In the event that a serious breach is suspected the Sponsor should be informed within 24 hours.

#### 22 Publications policy

The Investigators will be involved in reviewing drafts of the manuscripts, abstracts, and any other publications arising from the study. PIs will have final sign off on press releases. Authors will acknowledge that the study was "Funded by the NIHR Health Technology Assessment Programme". Authorship will be determined in accordance with the ICMJE guidelines and other contributors will be acknowledged. GLINT participants will be informed of the outcome of the study via a newsletter.

# 24 Appendices

## 24.1 Appendix 1 Schedule of procedures

	Recruitment	Visit 1			Visit 2		Visit 3		
		Baseline	4	8	3	4	6	Annual GP /	End of
		(day 0) [2]	wks	wks	month	month	month	participant	study /
					visit*	mail-	visit*	questionnaire	early
						out*		[6]	termination
Demographic information (DOB, sex,	Х	Х							
ethnicity)									
Medical history information (including diabetes, CVD, cancer)	Х	Х							
Biochemistry: HbA 1c , TC, LDL, HDL,		X (if value n/a in past			Х		Х		
triglycerides		12 months)							
Biochemistry: Creatinine		X (if value n/a in past			Х		Х		
		6 months)							
Blood pressure		Х							
Modelled ten-year cardiovascular risk		X (if value n/a in past							
(QRISK2/Framingham)		12 months)							
Anthropometry: height, weight		Х							
Informed consent and stored blood sample		Х							
authorisation									
Randomisation		X [3]							
If consent obtained, a whole blood sample		Х							
will be taken for storage for future DNA									
analysis, and a serum and plasma sample									
for biomarker analyses									
Letter / lifestyle booklet / emergency card		Х							
sent to participant if inclusion criteria met;									
letter sent to GP informing them individual									
is in study									
Drug dispensation		X [4,5]							
Phone call to check titration competency and			Х	Х					
adverse events									
Feasibility phase									
HbA 1c , creatinine		X [7]			Х		Х		
B12 levels, LFTs, total cholesterol, LDL and		X [7]					Х		
HDL cholesterol									

GLINT Protocol

Version Date: 18/03/2016

	Recruitment	Visit 1 Baseline (day 0) [2]	4 wks	8 wks	Visit 2 3 month visit*	4 month mail- out*	Visit 3 6 month visit*	Annual GP / participant questionnaire [6]	End of study / early termination
Medication count					Х		Х		
Questionnaire sent to participant / GP						Х			
Participant questionnaire									
Self-reported morbidity (CVD, cancer, T2DM)		Х				Х		Х	Х
Medication adherence						Х		Х	Х
Health service use in past 12 months (adapted from HERC questionnaire)		Х				Х		Х	Х
EuroQol EQ-5D		Х				Х		Х	Х
Treatment satisfaction / SF-8						Х		Х	Х
Adverse events / side-effects					Х	Х	Х	Х	Х
GP questionnaire									
Vital status						Х		Х	Х
Morbidity (CVD, cancer, T2DM)						Х		Х	Х
Current prescribed medication						Х		Х	Х
Adverse events						Х		Х	Х
Whether participant has become pregnant						Х		Х	Х
Endpoint ascertainment									
ONS/national registry tagging for ICD-10 coded mortality		Х							
National cancer registry tagging		Х							
Hospital Episode Statistics		Х							

[1] Potential recruiting routes: Individual is flagged by NHS Health Checks as (potentially) meeting inclusion criteria; Individual is identified by research database as (potentially) meeting inclusion criteria; Individual is identified by GP records as (potentially) meeting inclusion criteria

[2] Visits 1 and 2 may be, but are not required, to be performed on the same day

[3] Randomisation may be delayed up to 14 working days if complete data to assess eligibility is not available at visit 1.

[4] Participant receives batch of metformin / placebo every 16 weeks

[5] Participants who terminate study medication will continue to be observed and sent annual questionnaires according to their planned schedule for the remainder of the study.

[6] Reminders about postal questionnaires to be sent 4 and 8 weeks after initial posting; annual questionnaires to continue until study closeout

[7] During the feasibility phase, these measures will be taken for all participants at the recruitment visit

\*these measures will only be taken in the feasibility phase of the study

GLINT Protocol Version Number: 5.0 Version Date: 18/03/2016

# 24.2 Appendix 2 Modified Safety Reporting

All SAEs listed below are exempted from routine SAE reporting. However they will be assessed for relatedness to the study drug and if the event is considered related and not expected *i.e.* it is a SUSAR it will be reported in an expedited manner.

All SAEs not listed below will be reported as per standard guidelines and processes. In addition a quarterly line listing of these SAEs will be submitted to the sponsor.

1. Primary and secondary study endpoints

These events will prompt the investigator to complete an endpoint package which will then be adjudicated according to the Clinical Events Classification (CEC) charter:

-Cardiovascular (CV) death e.g. fatal myocardial infarction [MI]/cerebrovascular accident [CVA]/ congestive heart failure [CHF]/arrhythmia, cardiac arrest, death following CV intervention

-Non-fatal MI

-Acute coronary syndrome

-Non-fatal CVA

-CHF requiring hospitalization

-Unstable angina requiring hospitalization

-All cause mortality

2.Other Cardiovascular Events of Interest

-Atrial fibrillation/Atrial flutter

-Ventricular fibrillation/tachycardia requiring intervention

-Deep Vein Thrombosis (DVT)

-Pulmonary embolism

-Percutaneous Coronary Intervention (PCI) – (including non-serious events)

-Coronary Artery Bypass Graft (CABG)

-Coronary catheterization

-Stress test (including non-serious events)

-Abdominal aortic aneurysm/repair

-Carotid endarterectomy/ carotid angioplasty and/or stenting

- Any hospitalization due to cardiovascular events (i.e., whether or not the hospitalisation was for an obvious study endpoint)

-Shock/hypotension

-Accelerated or malignant hypertension/hypertensive urgency

-Transient Ischemic Attack (TIA)

-Syncope

-Renal artery angioplasty and/or stenting

-Other arterial angioplasty and/or stenting

3.Non-cardiovascular events of interest

Any non-melanoma incident cancer

Any non-melanoma recurrent cancer

Death due to cancer (any non-melanoma type) Physician diagnosed T2DM

4.Known adverse reactions of metformin

-GI upset / diarrhoea

-Hypoglycaemia

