# 12.2.1 Expected Adverse Reactions/Serious Adverse Reactions (AR /SARs)

The common side effects of metformin include GI upset and diarrhoea. Hypoglycaemia does occur rarely and lactic acidosis is a very rare but serious adverse effect.

Evidence from participants with NDH in the DPP suggests that hypoglycaemia is not expected and serious adverse effects will be very rare [18]. GLINT participants will be

advised about the symptoms suggestive of hypoglycaemia (such as tachycardia, palpitations, shakiness, sweating, inability to concentrate, dizziness, hunger, blurred vision, obvious impairment of motor function, confusion or inappropriate behaviour which reverse after intake of carbohydrates) and how to respond. Serious hypoglycaemia (requiring the assistance of another person) will be regarded as a serious adverse event triggering the safety reporting mechanism described in section 11.5 below. Each participant will be issued with a card indicating that he/she is participating in a research study. This card will indicate the name and the phone number of the investigational site to be contacted in case of an emergency, including any episode of suspected hypoglycaemia requiring the assistance of another person. The card will also specify temporary interruption of treatment with study medication if participants undergo general anaesthesia or investigation with iodine-containing X-ray contrast media, and if participants are at risk of tissue hypoxia or sudden deterioration in renal function, for example due to severe dehydration or infection, shock, sepsis, acute heart or respiratory failure, hepatic impairment and recent myocardial infarction.

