#### 12.4 Recording and evaluation of adverse events

#### Non-serious Adverse Events

AEs will only be recorded if they result in cessation of the drug and the event is considered related to the drug.

The following information will be recorded: description of event, date of onset, dosage and any required changes, assessment of seriousness, assessment of expectedness, relevant medical history, concomitant medications, causality assessment and resolution/outcome.

**Serious Adverse Events** All events that fulfil the criteria for serious will be collected and reported, however those detailed in Appendix 2 will be subject to a modified safety reporting plan. These events include (1) Primary and secondary study endpoints, (2) Other cardiovascular events of interest (that may be associated with the primary CV endpoints and are included among items that will be sent for review by the CEC), (3) other non-cardiovascular events of interest (e.g. incident cancer, incident T2DM), (4) known common toxicities of metformin.

Any SAE which is not listed in appendix 2 will be recorded using the AE/SAE eCRF.

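### Appendix 2 exempts every death from routine SAE reporting but requires standard reporting of unlisted SAEs, and does not say which rule governs a death caused by an unlisted SAE such as lactic acidosis

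*Protocol*

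**What the plan says.** Appendix 2 sets the modified reporting plan. It opens with "All SAEs listed below are exempted from routine SAE reporting". Item 1 of the list (primary and secondary endpoints) names cardiovascular death and, separately, "All cause mortality". Item 3 adds death from any non-melanoma cancer. Item 4, headed "4.Known adverse reactions of metformin", has two entries only: gastrointestinal upset or diarrhoea, and hypoglycaemia.

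Listed events keep one safeguard: "However they will be assessed for relatedness to the study drug and if the event is considered related and not expected", the event is handled as a SUSAR and expedited.

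For everything else the appendix says "All SAEs not listed below will be reported as per standard guidelines and processes". The next sentence adds a quarterly line listing to the sponsor. Section 12.4 agrees: "Any SAE which is not listed in appendix 2 will be recorded using the AE/SAE eCRF".

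On expectedness, section 12.2.1, whose title labels its contents as expected reactions, says "Hypoglycaemia does occur rarely and lactic acidosis is a very rare but serious adverse effect". Section 12.3 describes the events in Appendix 2 as expected. The formal test lies elsewhere. Section 12.2 makes section 4.0 of the SmPC the reference safety information, and section 12.1.3 treats a reaction as unexpected if its nature, severity or outcome does not fit that reference.

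**The concern.** An exemption of this kind is normally meant for endpoints and expected background events. The entry for all-cause mortality reaches further. Cardiovascular deaths and non-melanoma cancer deaths are already on the list, so what the entry mainly adds is the remaining deaths. A death from a drug reaction or another unanticipated cause would fall in that group.

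Lactic acidosis shows the problem most clearly. Section 12.2.1 gives its raised risk in chronic kidney disease as the reason for excluding people with low eGFR and for measuring creatinine in the feasibility phase. Item 4 leaves it off the exempt list, so a non-fatal case is reported in full. The mortality entry can reverse that for a fatal case, and the worse outcome may then receive less reporting. The same applies to any other death whose cause is not listed.

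At stake is whether the sponsor receives such a case through the routine SAE route and its quarterly listing.

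**Working it through.** The protocol states no figure on this point and there is nothing to compute. The check follows one case, a fatal lactic acidosis judged related to study drug, through the rules.

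1. **Is it listed?** As a death, yes (Appendix 2, item 1, no restriction by cause). As a diagnosis, no (item 4 has only the two reactions named above, and no other item covers it).
2. **What follows from each answer?** Listed means exempt from routine reporting. Unlisted means standard reporting (Appendix 2, 12.3) and the AE/SAE eCRF (12.4). The two instructions are opposite.
3. **Does any section set precedence?** No. Section 12.1.4 makes death a criterion of seriousness, which favours filing by the underlying event. But Appendix 2 itself lists mortality as an event, and section 12.4 puts primary and secondary endpoints, which include all-cause mortality, under the modified plan. Section 12.5 refers reporting timelines back to Appendix 2.
4. **If it is filed as a listed death, does the SUSAR safeguard catch it?** Only if it is judged unexpected. The title of 12.2.1 and the wording of 12.3 point towards expected. The outcome rule in 12.1.3 could make a fatal outcome unexpected, depending on SmPC text that the protocol does not reproduce.
5. **Does the quarterly listing catch it?** The sentence refers back to the SAEs just mentioned, which are the unlisted ones. Read literally, an exempt death is left out. If the listing was meant to cover exempt events as well, the wording does not say so.

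The outcomes side by side:

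| Step | Non-fatal case | Fatal, filed by cause | Fatal, filed as death, judged expected | Fatal, filed as death, judged unexpected |
|---|---|---|---|---|
| Routine SAE reporting | Yes | Yes | No | No |
| AE/SAE eCRF form (12.4) | Yes | Yes | Not required by 12.4 | Not required by 12.4 |
| Expedited as SUSAR | Only if unexpected | Only if unexpected | No | Yes |
| Quarterly listing, literal reading | Yes | Yes | No | No |
| Recorded in eCRF, study team notified (12.5) | Yes | Yes | Yes | Yes |
| Adjudicated as a death (13, 17.4) | Not applicable | Yes | Yes | Yes |
| Open to IDMC review (17.3) | Yes | Yes | Yes | Yes |

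The gap is confined to one column: filed as the listed death and judged expected. The protocol permits that column but does not require it.

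**The case against.** The strongest reply is that the gap appears only if the death, rather than its cause, is filed as the event. Under 12.1.4 an SAE is an occurrence that results in death. On that view the event is the lactic acidosis, it is unlisted, and 12.3, 12.4 and Appendix 2 all send it down the standard route. This is a reasonable reading, and it rules out saying that a fatal case is bound to be missed. It does not remove the defect, because Appendix 2 also lists the death itself and nothing tells a site which reading to use.

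A second reply is that expectedness is judged against the SmPC, including outcome, and not against the prose of 12.2.1. That is correct. A related fatal case may prove to be a SUSAR and be expedited. Whether it would cannot be settled from the protocol.

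A third reply is that nothing is lost. Section 12.5 has all SAEs recorded in the eCRF with immediate notice to the study team, listed events are still assessed for relatedness, deaths are adjudicated, and the IDMC reviews SAEs. This stands as far as the data are concerned. A reader might infer that fatal cases vanish from the SAE dataset, or that safety tables would understate the harm. The protocol does not support either inference. But recording is not reporting. The adjudication described in 13 and 17.4 concerns endpoints, and drug causality is not a stated task of that committee. The IDMC sees an agreed subset of the data set out in its charter. Neither is a stated replacement for routine reporting to the sponsor.

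**Conclusion.** The point holds as an unresolved conflict in a stated rule. A death caused by an SAE outside Appendix 2 is both exempt and reportable, and no section decides between the two. On one permitted reading, a related fatal reaction judged expected escapes routine SAE reporting, expedited reporting and, taken literally, the quarterly listing.

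The stronger statement, that fatal lactic acidosis necessarily falls outside both routes, does not hold. It would require that the case be filed as a death and that a fatal outcome be consistent with the SmPC. The protocol settles neither.

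The possible loss is routine sponsor reporting and listing for deaths that are neither cardiovascular nor due to a cancer or other cause on the list. No count can be attached to it. The protocol calls lactic acidosis very rare without giving a rate and gives no case fatality, so any figure would rest on assumption alone. The point deserves action because it concerns possible drug-related deaths and can be resolved with one edit.

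**What to change.** State in Appendix 2 which rule governs. Either of two changes would do:

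- limit the mortality exemption to deaths whose cause is itself a listed event; or
- keep the entry and add that a death caused, or suspected to be caused, by an SAE not listed in Appendix 2 follows the route for unlisted SAEs: the AE/SAE eCRF, standard reporting and the quarterly listing.

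At the same time, make clear which SAEs the quarterly listing covers, and reconcile the appendix with 12.1.3, 12.2.1, 12.3, 12.4 and 12.5. In particular, the description of Appendix 2 events as expected in 12.3 should not be open to use in place of the SmPC test. All-cause mortality stays an adjudicated secondary endpoint, so no analysis changes.

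The same revision should look at hypoglycaemia, which is a separate conflict: 12.2.1 says a serious episode triggers the safety reporting mechanism, while item 4 lists hypoglycaemia as exempt. Limiting the exemption to deaths from a listed cause would carry that conflict over to a death from hypoglycaemia.

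The cost is one list entry or one sentence, plus some additional SAE forms for non-cardiovascular, non-cancer deaths. Deaths are already documented for adjudication, so the extra work should be small.

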**GLINT Protocol** 

Version Date: 18/03/2016
